A randomized, double-blind, placebo-controlled clinical trial of three pharmacological groups will be carried out, with the participation of 34 patients with a recent diagnosis of DM2 according to the criteria of the American Diabetes Association.¹⁶ The propolis capsules

will be obtained from NOW® of Chicago, Illinois (USA), containing 300 mg of propolis powder. Calcined magnesia will be used for the placebo. The allocation will be done by simple randomization using a list of numbers. All patients will receive for 12 weeks one capsule before the first bite of breakfast and another before the first bite of dinner. 12 of them took propolis (300 mg twice a day), another 12 received metformin (850 mg twice a day) and 12 more, placebo in the same pharmacological presentation. Each participant will receive medical nutritional therapy and will be instructed to continue with their normal physical activity.

Clinical and laboratory measurements

The medical history of each patient will be taken and anthropometric indices will be measured that included: height, weight, BMI, waist circumference (WC) and percentage of fat mass. In addition to blood pressure. Five visits will be completed during the study and a 2-h oral glucose tolerance test (OGTT) will be performed at the beginning and end of the intervention to calculate the areas under the curve (AUC) of glucose and insulin, total insulin secretion (insulinogenic index), first phase of insulin secretion (Stumvoll index) and insulin sensitivity (Matsuda index). For this, the individuals will take a solution with 75 g of anhydrous glucose dissolved in 300 ml of water in 5 minutes. After that, blood samples will be taken through a heparinized catheter before and at 30-min intervals (30, 60, 90 and 120 minutes) for 2 hours. At each visit, the presence of adverse events will be verified through the diary and compliance through the capsule count.

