To calculate low-density cholesterol, the Friedewald formula will be used: $LDL-c \text{ (mmol/L)} = TC \text{ (mmol/L)} - HDL-c \text{ (mmol/L)} - [TG \text{ (mmol/L)} / 2.2]$, while for very low density cholesterol (VLDL) the ratio of $TG \text{ (mmol/L)} / 2.2$ will be used. With a liquid chromatography the percentage of A1C will be calculated. The AUC of glucose and insulin will be calculated with the polygonal formula. Total insulin secretion will be assessed with the insulin index: $(\Delta AUC \text{ of insulin}) / (\Delta AUC \text{ of glucose})$. With the Matsuda $10000 / \sqrt{[(Glucose_0 \cdot Insulin_0) (Average \text{ of the PTOG} \cdot Average \text{ of the insulin in the PTOG})]}$ index the insulin sensitivity will be estimated, while with the index from Stumvoll $1283 + 1.829 \times \text{insulin}_{30'} - 138.7 \times \text{glucose}_{30'} + 3.772 \times \text{insulin}_0'$, the first phase of insulin secretion.

Sample size

For this study, the sample size it's calculated using a formula for mean difference¹⁷ with a statistical confidence of 95%, a statistical power of 80%, a standard deviation (SD) and an expected difference for fasting glucose, A1C and 2-h glucose of 0.6 mmol/L¹² and 1.0 mmol/L⁹, 0.5% and 0.8%¹², 2.3 mmol/L¹⁸ and 3.9 mmol/L¹⁹, respectively. While for metformin it's of 2.4 mmol/L²⁰ and 3.0 mmol/L²¹, 1.0% and 1.5%²², 3.5 mmol/L²³ and 5.5 mmol/L²⁴, respectively. A total of 12 patients is obtained for each group, including 20% of the expected loss.

Security measures

All patients will be informed about the possible adverse effects of propolis and metformin; they will have the emergency telephone numbers of the responsible and associated investigators.

STATISTIC ANALYSIS

The study will be designed to demonstrate the effect of propolis and metformin relative to placebo in terms of the outcome variables of effectiveness. Assuming there are no differences in propolis and metformin versus placebo regarding effectiveness in reducing glycemic control, it's calculated that approximately 36 randomized patients will provide ~80% power to demonstrate superiority.

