All statistical analyzes will be performed by intention to treat, which will be included randomized patients who receive at least 1 dose of study treatments and for whom there has a baseline value on measurements. First, with the Kruskal-Wallis test, it will be tested whether the baseline data group of primary and secondary variables come from the same population, that is, whether the 3 groups are comparable as no statistically significant differences are found.

Then, using the Kruskal-Wallis test, the final data will be evaluated and with those that will be significant a post-hoc test (Mann Whitney U) will be performed, comparing propolis versus metformin, propolis versus placebo, and metformin versus placebo. Differences between baseline and final measurements for primary and secondary variables will be calculated with the Wilcoxon test. Statistical comparisons will be made using a comparative type 1 error of 5% (two-tailed).

The safety profile analysis will include patients who receive at least 1 dose of study medication; safety data will be summarized using descriptive statistics.

FINANCING

The financing will be by own resources of the University of Guadalajara.

REFERENCES

1. IDF (International Diabetes Federation). International Diabetes Federation. Vol. 9, International Diabetes Federation. 2019. 144 p.
8. Khalil M. Biological activity of bee propolis in health and disease. *Asian Pac J Cancer Prev APJCP.* 2006;7:22–31.

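### The stated ~80% power belongs to a comparison of means; for metformin fasting glucose, which sets the sample size, the planned two-step rank test gives about 61–67% with 10 evaluable per group

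*Combined protocol and SAP*

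**What the plan says.** The Sample size section uses a two-sample formula for a difference in means, at 95% confidence and 80% power. For each active drug it lists an SD and an expected difference for fasting glucose, A1C and 2-h glucose, and concludes: "A total of 12 patients is obtained for each group, including 20% of the expected loss". It does not say which of the six pairs sets the size or how the 20% was applied.

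The Statistic Analysis section says that "approximately 36 randomized patients will provide ~80% power to demonstrate superiority", and opens that sentence with the premise "Assuming there are no differences in propolis and metformin versus placebo".

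The analysis described there is not a comparison of means: "using the Kruskal-Wallis test, the final data will be evaluated and with those that will be significant a post-hoc test (Mann Whitney U"), for the three pairwise comparisons, each at a two-sided 5% level. No power check for these rank tests is reported.

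The Study design section describes a trial "with the participation of 34 patients" and then lists three groups of 12.

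**The concern.** The power was worked out for one procedure and the data will be analysed by another. A pairwise result counts only if two tests succeed in turn: Kruskal-Wallis across three arms, then Mann-Whitney for the pair. At about 10 patients per arm, the normal approximation, the change to ranks and the gate each lower power relative to the formula.

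The plan also uses two SDs for fasting glucose, 0.6 mmol/L for propolis and 2.4 mmol/L for metformin, although both drugs are compared with the same placebo arm. The power sentence is worded as if 80% applied under no difference.

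At stake is how a non-significant result will be read. If power is overstated, such a result looks more informative than it is, even for metformin, which the introduction treats as the reference treatment.

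**Working it through.** **1. Reproducing 12 per group.** With n = 2(1.96 + 0.8416)² × SD²/difference², the Sample size inputs give:

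| Input | SD | Difference | n per group |
|---|---|---|---|
| Propolis, fasting glucose (mmol/L) | 0.6 | 1.0 | 5.65 |
| Propolis, A1C (%) | 0.5 | 0.8 | 6.13 |
| Propolis, 2-h glucose (mmol/L) | 2.3 | 3.9 | 5.46 |
| Metformin, fasting glucose (mmol/L) | 2.4 | 3.0 | 10.05 |
| Metformin, A1C (%) | 1.0 | 1.5 | 6.98 |
| Metformin, 2-h glucose (mmol/L) | 3.5 | 5.5 | 6.36 |

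The largest is 10.05. Taken as 10, 10 × 1.2 = 12, the stated figure. Stricter handling gives 10.05/0.8 = 12.6, so 13; or 11/0.8 = 13.75, so 14.

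**2. Reproducing ~80%.** For that pair d = 3.0/2.4 = 1.25. At 10 per group, d√(n/2) = 1.25 × √5 = 2.795; 2.795 − 1.96 = 0.835; Φ(0.835) = 79.8%. This matches the plan.

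**3. Evaluable patients.** 12 × 0.8 = 9.6, so about 10 per group.

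**4. Same comparison, other tests.** The t-test (noncentral t, d = 1.25) has 75% power at 10 per group and 73% at 9.6. Mann-Whitney alone, exact, two-sided 5%, has about 71% at 10 and 80% at 12.

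**5. The planned sequence.** I simulated Kruskal-Wallis at 5% followed by exact Mann-Whitney for metformin versus placebo, requiring both to be significant. Data were normal, with SD 2.4 in the metformin and placebo arms and a metformin difference of 3.0 (20,000 trials per setting). The SDs are assumed to apply to the final values, which are what the plan tests. The third arm affects the gate, so its assumptions were varied:

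| Propolis arm | 10 per group | 12 per group |
|---|---|---|
| Difference 1.0, SD 2.4 | 61% | 71% |
| Difference 0, SD 2.4 | 65% | 76% |
| Difference 1.0, SD 0.6 | 67% | 77% |

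A propolis difference of 1.5 with SD 2.4 gives 70% at 12. Other propolis-arm assumptions, or the asymptotic Mann-Whitney p-value, widen the range at 10 to about 60–70%.

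**6. Other endpoints, planned sequence, 10 per group.** With the metformin SD in all arms, metformin versus placebo has about 77% for A1C and 83% for 2-h glucose. Propolis versus placebo on fasting glucose has about 12% if the SD is 2.4 in all arms and about 91% if it is 0.6 in all arms.

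**7. The power premise.** If neither drug differs from placebo, the chance that a given comparison is significant is at most about 5%, the test level. It cannot be 80%.

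**8. Total.** 12 + 12 + 12 = 36, not 34.

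**The case against.** The strongest defence is that the sample size reproduces. A reader might infer from the stricter results of 13 or 14 that 12 does not follow from the plan's formula. The documents do not support that: they say only that 20% loss is included, without committing to division by 0.8. The gap is a rounding and inflation convention worth 1 to 2 patients per group.

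A reader might also take 61–67% as the power of the whole trial. It is not. It belongs to one drug and one endpoint, the most demanding of six inputs, and rests on normal data and an assumed SD for each arm. The plan gives no common SD. With SD 0.6 in both the propolis and placebo arms, metformin fasting-glucose power at 10 per group would be about 91%. But the 10.05 that yields 12 per group uses 2.4 for both arms of the metformin comparison, so that case departs from the plan's own sizing calculation. Likewise, quoting only the low propolis figure would be one-sided: about 12% and about 91% both follow from SDs that the plan uses.

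The evaluable number can be disputed too. The intention-to-treat definition requires only one dose and a baseline value, so 12 per group might contribute. However, the Selection criteria section removes patients with poor adherence or tolerability, no method for missing final values is given, and the plan itself expects 20% loss. Even with all 12, the two-step power in the settings above is 70–77%.

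Finally, the premise of no difference is probably a clumsy statement of the null hypothesis, since the assumed differences appear under Sample size. That makes it a wording error rather than evidence that the size was calculated under the null. As written, it still contradicts the claim it introduces.

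**Conclusion.** The sample size stands; the stated power does not hold for the comparison that sets it. For metformin versus placebo on fasting glucose, with SD 2.4 in both arms, the planned tests give about 61–67% at 10 evaluable per group, which is 13 to 19 points below the 79.8% from the formula. Part of the loss comes from the normal approximation (75% by t-test), part from the change to ranks (about 71%), and the rest from the Kruskal-Wallis gate.

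The size of the shortfall depends on the propolis-arm assumptions and does not extend to every endpoint: metformin 2-h glucose is above 80% and A1C only slightly below. For propolis on fasting glucose, the plan's two SDs leave power undetermined. The premise of no difference and the 34 against 36 mismatch are textual errors that need no simulation.

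**What to change.** - Keep 12 randomised per group. State that 10.05 was taken as 10 and that the 20% was added by multiplication, leaving about 10 evaluable.
- Restate the power for the Kruskal-Wallis then Mann-Whitney sequence at that number: about 61–67% for metformin versus placebo on fasting glucose. Name the endpoint, the differences and the SD assumed in each arm, including the single placebo SD for fasting glucose. Give the corresponding propolis figure under the same SDs.
- Replace the premise of no difference from placebo with the assumed differences.
- Reconcile 34 patients in Study design with 3 × 12 = 36.

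The cost is wording and a less favourable stated power; no extra patients are needed. Changing the analysis method to recover power would be a separate decision and is not part of this correction.

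### The efficacy tests can use only patients with a final value, and the plan does not provide for collecting or handling missing ones, so an available-case result would carry an intention-to-treat label

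*Combined protocol and SAP*

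**What the plan says.** All references are to the combined protocol and SAP.

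- **Statistic Analysis, label and set.** "All statistical analyzes will be performed by intention to treat", in "randomized patients who receive at least 1 dose of study treatments and for whom there has a baseline value on measurements". No post-baseline value is required.
- **Statistic Analysis, efficacy tests.** Between groups: "using the Kruskal-Wallis test, the final data will be evaluated", with pairwise Mann-Whitney U tests where that is significant. Within groups: "Differences between baseline and final measurements for primary and secondary variables will be calculated with the Wilcoxon test". The only other test is on baseline data and is a comparability check, not an efficacy test.
- **Clinical and laboratory measurements.** The oral glucose tolerance test (OGTT) "will be performed at the beginning and end of the intervention". There are five visits, but the text does not say at which of them fasting glucose or A1C is measured.
- **Study design.** Treatment lasts 12 weeks, so the final value is a week-12 value.
- **Sample size.** The 12 per group is given as "including 20% of the expected loss". What that loss consists of is not stated.
- **Selection criteria.** Patients with poor tolerability, adherence below 80%, a serious adverse event or withdrawn consent are to be eliminated. The text does not say whether this means from treatment or from the analysis.

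No section gives a rule for missing final values, a sensitivity analysis, or week-12 measurement of patients who stop early.

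**The concern.** The set is defined by what happens at the start of the trial, and the tests by what is available at the end. A patient who takes one capsule and never returns belongs to the set but contributes to no efficacy test. Rank tests on final data leave such a patient out unless a rule says otherwise, and there is none.

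Two things are at stake. The first is the label: readers would take the result to describe everyone treated when it describes those who were measured. The second is bias. If the reasons for leaving differ by arm and relate to glucose, the arms compared at week 12 are no longer the arms that were randomized. With 12 per arm, two selective losses can move the answer.

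**Working it through.** **1. The plan's own figure.** Inputs from Sample size: metformin fasting glucose, SD 2.4 and difference 3.0 mmol/L, two-sided 5%, power 80%. This pair gives the largest n of the six listed.

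n = 2 × [2.4 × (1.960 + 0.842) / 3.0]² = 10.05 per group. Rounded to 10, 10 × 1.2 = 12, as stated. The design therefore counts on about 10 patients per arm with a final value, not 12.

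**2. Who can enter each test.**

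| Test | Needs | Patient with baseline only |
|---|---|---|
| Kruskal-Wallis, baseline | baseline value | included (not efficacy) |
| Kruskal-Wallis, final | final value | left out |
| Mann-Whitney U, final | final value | left out |
| Wilcoxon, baseline to final | both values | left out |

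For 2-h glucose, the AUCs and the insulinogenic, Stumvoll and Matsuda indices, no interim value exists to stand in.

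**3. How many.** 0.20 × 36 = 7.2, or 0.20 × 12 = 2.4 per arm. If all of the loss meant no final value, about 29 of 36 would be analysed.

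**4. Worst case for placebo.** Assume normal data and that placebo loses exactly its two highest of 12 values. The mean of the lowest 10 of 12 standard normal values is about −0.27 (simulated: −0.273 to −0.275).

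- Shift at SD 2.4: 0.273 × 2.4 = 0.66 mmol/L.
- Against the planned metformin difference: 0.66 / 3.0 = 22%.
- On the plan's propolis fasting-glucose pair (SD 0.6, difference 1.0): 0.273 × 0.6 = 0.16 mmol/L, or 16%.
- Mann-Whitney power, metformin against placebo, 10 per arm, effect 3.0 / 2.4 = 1.25 SD: 70 to 71% with random loss and 57 to 58% with the selective loss (range over independent simulations).

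The selective pattern accounts only for the drop from about 71% to 57%. The starting 71% already reflects 10 per arm and the rank test; with 12 per arm, simulated power is about 80%.

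**5. Worst case for an inert propolis arm.** Propolis loses its two worst of 12, and the other arms lose two at random. Chance of a significant Mann-Whitney result favouring propolis over placebo:

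| Condition | Random loss | Selective loss |
|---|---|---|
| No Kruskal-Wallis step first | 2.2% | about 9% |
| Kruskal-Wallis first, no arm works | about 1% | about 5% |
| Kruskal-Wallis first, metformin works (1.25 SD) | about 2% | about 8% |

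The plan requires the Kruskal-Wallis step, so the lower two rows apply to it. The nominal rate in one direction is 2.5%.

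**6. Would imputation from baseline repair this?** If the two highest final values are lost, within-arm regression imputation leaves a shift of about −0.25, −0.22 or −0.16 SD at assumed baseline-final correlations of 0.3, 0.5 and 0.7, against −0.27 with no imputation. Most of the bias remains.

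**The case against.** **The 20% allowance already deals with dropout.** It protects power. It does not protect against selective loss, and it does not turn an analysis of those measured into intention to treat.

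**The 20% may not be missing data.** This stands. A reader might infer that 7 of 36 patients will have no final value. The documents do not support that: the make-up of the expected loss is not stated, and the eliminations under Selection criteria may form part or all of it. The 7 is an upper figure at the planned rate, and actual loss may differ.

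**The set and the tests are not strictly incompatible.** This also stands. A reader might conclude that the plan prescribes a completers' analysis. It does not say so; that outcome follows from its silence. Fasting glucose or A1C could have been taken at some of the five visits and carried forward, but the plan neither schedules nor proposes this, and for OGTT outcomes it is not possible.

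**Selective loss is assumed.** Correct. A reader might infer that patients will leave for reasons that reveal their arm. The trial is double-blind with matched presentation, and no section names a reason for leaving that is tied to arm or to glucose. If loss only became likelier with higher values (log-odds slope 0.5 to 1 per SD, an assumption), the shift would be 0.08 to 0.15 SD rather than 0.27.

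**Conclusion.** The point holds as a gap between label and analysis. The plan promises intention to treat for every dosed patient with a baseline value, names only efficacy tests that need a final value, expects losses, and does not say how final values will be obtained or what happens without them.

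The possible size is moderate and depends on the pattern of loss. In the extreme pattern examined, the placebo mean shifts by 0.27 SD, metformin-placebo power falls from about 71% to 57%, and under the plan's test sequence a false result favouring an inert propolis arm rises to about 5% if no arm works and about 8% if metformin works. These figures assume normal data, 10 of 12 per arm analysed, and loss fully determined by the final value. They show how far the result could move and do not predict that it will. A reader might be tempted to set the 0.66 mmol/L shift against the planned propolis difference of 1.0 mmol/L, but that joins metformin's SD to propolis's difference; the plan's own propolis pair gives 16%.

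This should be corrected before analysis; it does not undermine the design.

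**What to change.** 1. Ask every dosed patient who still consents for the week-12 fasting sample, A1C and OGTT, whether or not capsules were stopped, and analyse the values in the assigned arm. This does most of the work, because it removes the gap at its source.
2. For each test, report the number with a final value per arm. Label any analysis restricted to those patients as available-case or completers.
3. For values still missing, pre-state a sensitivity analysis that allows worse outcomes in those lost. Worst-rank assignment is one example and suits the planned rank tests; the worst direction needs defining for each variable. Within-arm imputation from baseline should not be the main result, since it leaves most of the illustrated bias.
4. Reconcile the elimination wording in Selection criteria with the intention-to-treat statement in Statistic Analysis, saying whether elimination is from treatment or from analysis.

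The cost is a few end-of-study visits for patients who stop early, some SAP wording and slightly more analysis. The sample size does not change. The estimated effect may be smaller if patients who stop respond less.

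### The between-arm tests leave out the baseline values already collected: the planned analysis is valid but inefficient, and the ~80% power holds only under unstated SD assumptions

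*Combined protocol and SAP*

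**What the plan says.** **Between-arm analysis (Statistic analysis).** For each variable, "using the Kruskal-Wallis test, the final data will be evaluated and with those that will be significant a post-hoc test" follows, namely Mann-Whitney U on the three pairs, each at two-sided 5%.

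**Use of baseline (same section).** Baseline appears in a Kruskal-Wallis test of whether the arms are comparable and in a Wilcoxon test of baseline against final values. No covariate, change score or other use of baseline enters a comparison between arms. The intention-to-treat set is limited to treated patients "for whom there has a baseline value on measurements". The glucose tolerance test "will be performed at the beginning and end of the intervention" (Clinical and laboratory measurements).

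**Aim and power.** The trial is to "demonstrate the effect of propolis and metformin relative to placebo in terms of the outcome variables of effectiveness", and "approximately 36 randomized patients will provide ~80% power to demonstrate superiority".

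**Sample size.** A two-mean formula is applied to six pairs of SD and difference. The propolis list begins "an expected difference for fasting glucose, A1C and 2-h glucose of 0.6 mmol/L"; the metformin list begins "While for metformin it's of 2.4 mmol/L". The result: "A total of 12 patients is obtained for each group, including 20% of the expected loss".

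**The concern.** With about 12 patients per arm, precision is scarce. A baseline measurement of the same variable usually predicts its final value, and this plan collects it on everyone it will analyse. Leaving it out of the between-arm test gives up precision at no saving.

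The power statement comes from a two-mean formula, whereas the analysis is a three-arm Kruskal-Wallis gate followed by a rank test. If the two differ materially on the pair that drives the sample size, the trial could miss a planned metformin effect on fasting glucose more often than the intended 20% of the time.

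**Working it through.** **Inputs.** From Sample size (SD, then difference): propolis fasting glucose 0.6 and 1.0 mmol/L, A1C 0.5% and 0.8%, 2-h glucose 2.3 and 3.9 mmol/L; metformin fasting glucose 2.4 and 3.0 mmol/L, A1C 1.0% and 1.5%, 2-h glucose 3.5 and 5.5 mmol/L. Two-sided 5%, 80% power, 12 per arm including 20% loss (about 10 completers). The documents do not say whether an SD is of final values or of change, or whether it applies to every arm, and they give no baseline-final correlation r. These are assumptions below.

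**Step 1: the plan's own figure.** n per arm = 2 × [(1.960 + 0.842) × SD / difference]².

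| Pair | Propolis | Metformin |
|---|---|---|
| Fasting glucose | 5.65 | 10.05 |
| A1C | 6.13 | 6.98 |
| 2-h glucose | 5.46 | 6.36 |

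Only metformin fasting glucose needs about 10, and 10.05 × 1.2 = 12.06, so 12 per arm reproduces. Normal-approximation power is Φ(1.25 × √(n/2) − 1.96), where 1.25 = 3.0/2.4: 79.8% at n = 10 and 86.5% at n = 12. The ~80% reproduces.

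**Step 2: the planned rule on that pair.** Simulation with normal data, common final-value SD 2.4, chi-square Kruskal-Wallis gate, then exact Mann-Whitney for metformin versus placebo.

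| Method | 12 per arm | 10 per arm |
|---|---|---|
| Normal formula | 86.5% | 79.8% |
| t test | 83.3% | 75.3% |
| Mann-Whitney, no gate | 80% | 71% |
| Planned rule, propolis equal to placebo | 76% | 65% |
| Planned rule, propolis 1.0 mmol/L below placebo | 71% | 60% |

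No row uses baseline. The loss therefore comes from small samples, the rank test and the gate.

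**Step 3: what adjustment recovers.** Rank-based ANCOVA (Quade) as the gate, then for the pair; same assumptions; 12 / 10 per arm.

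| r | Propolis equal to placebo | Propolis 1.0 below |
|---|---|---|
| 0 | 75 / 65% | 71 / 60% |
| 0.3 | 79 / 69% | 74 / 64% |
| 0.5 | 86 / 76% | 82 / 72% |
| 0.7 | 95 / 89% | 93 / 86% |

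Against the planned rule the gains are 3-4 points at r = 0.3 (79 − 76, 69 − 65, 74 − 71, 64 − 60), 10-12 at 0.5 and 19-26 at 0.7. Reaching 80% needs r of about 0.34 / 0.57 in the first case and 0.47 / 0.63 in the second.

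**Step 4: other readings of the SDs.**
- Arm-specific SDs (assumed placebo and propolis 0.6, metformin 2.4): the planned rule gives about 95% / 90% for metformin versus placebo, so no shortfall.
- 2.4 as an SD of change: final SD = 2.4 / √(2(1 − r)), which is 2.03, 2.40 and 3.10 at r = 0.3, 0.5 and 0.7. With propolis equal to placebo, the planned rule gives 89/82%, 76/65% and 51/41%; rank ANCOVA gives 91/84%, 86/76% and 78/67%. At r = 0.3 with propolis midway between placebo and metformin, the planned rule gives 85/76%.

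**Step 5: the other five pairs.** The planned rule gives about 86-96% with 12 per arm and 77-91% with 10. The low end is metformin A1C; with propolis at its stated 0.8% effect and a common SD of 1.0% it has 86% / 77%.

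**Step 6: error rates, no effect anywhere, any false-positive pair.** Equal SDs: planned 4.5%, Quade 4.9%. SDs 0.6/0.6/2.4: 7% and 8%. The same SDs with completers 12/10/8, fewest on metformin: 8% and 10%.

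**The case against.** The strongest objection is about cause. A reader might infer that omitting baseline adjustment produces the shortfall. It does not: at r = 0 rank ANCOVA has the same power as the planned rule to within a point, and ungated Mann-Whitney with 12 per arm already gives 80%. This objection stands. Adjustment is a remedy of uncertain size, not the correction of the cause. Dropping the gate would also recover power (the adjusted test at r = 0.5, 10 completers and propolis 1.0 below placebo goes from 72% to 80%). With three arms, however, the gate is what holds the chance of any false-positive pair near 5% under equal SDs, so it is reasonable to keep it.

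Second, the shortfall depends on reading 2.4 mmol/L as a final-value SD common to all arms. Sample size lists different SDs for propolis and metformin and does not say which reading is meant. This also stands, and the power figures must carry that condition.

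Third, ANCOVA-type estimates can mislead when variances differ. A pooled-variance two-arm 95% CI covered about 89% with SDs 0.6 and 2.4 and completers 12 and 8. That is met by using robust standard errors.

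Fourth, the documents make no later analysis conditional on the baseline test and rest no stated efficacy claim on the Wilcoxon test. That is correct, so those two items are wording only.

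**Conclusion.** The point holds as one of efficiency and of an unconditional power statement. The between-arm tests are valid but discard information that every analysed patient supplies. Under a common final-value SD of 2.4 mmol/L, with propolis equal to placebo or 1.0 mmol/L below it, the planned rule has 71-76% power for metformin fasting glucose with 12 per arm and 60-65% with 10 completers. It would then miss the planned effect in 24-40% of trials.

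The documents do not support three stronger readings. The trial is not shown to be underpowered in general: with 12 per arm the other five pairs exceed 80%, and with 10 completers only metformin A1C falls slightly below it. The shortfall is not certain even for metformin fasting glucose, since it is absent with arm-specific SDs and, with propolis equal to placebo, if 2.4 is an SD of change with r about 0.3. And baseline is not unused; it is absent only from the comparison between arms.

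The gain from adjustment rests on r, which is not given. Confidence is medium for that reason and because of the SD ambiguity.

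**What to change.** Amend the Statistic analysis section as follows.

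1. **One prespecified method for every variable.** Rank final and baseline values over the three arms, regress final ranks on baseline ranks, and compare the residuals between arms at 5%. This replaces Kruskal-Wallis on final values as the gate. If it is significant, repeat for each pair after re-ranking within the pair, in place of Mann-Whitney.
2. **Avoid one pooled-variance three-arm ANCOVA for the contrasts.** With SDs 0.6/0.6/2.4 and r = 0.5 it has 38% / 28% power for propolis versus placebo (12 / 10 per arm), against 95% / 90% for the planned rule and 98% / 95% for rank ANCOVA.
3. **Name the contrasts that answer the aim:** propolis versus placebo and metformin versus placebo.
4. **Report size.** Give the baseline-adjusted two-arm difference with a 95% CI from heteroscedasticity-robust standard errors, in a small-sample form such as HC3. The rank test decides significance.
5. **Restate the ~80%.** Say whether each SD is of final values or change and whether it is common to the arms, and tie the power to the analysis actually used.
6. **Optional wording.** Call the Wilcoxon and baseline results descriptive. All arms receive nutritional therapy, so a within-arm fall does not show an effect relative to placebo, and a non-significant baseline test at 12 per arm does not establish comparability.

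**Cost.** Text changes only, with no new visits, samples or exclusions. Up to 1 point of power is lost if r is 0. Any-pair false positives rise by 1 to 2 points if SDs are very unequal (8% versus 7%, or 10% versus 8% with unequal completers). If all SDs are equal, the rank method gives about 3 to 5 points less power than two-arm ANCOVA, which is the price of protection when they are not.
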